8.5.2. Primary Objective #2

Evaluate the impact of the intervention on SND subjects receiving an indicated IPG device.

This document is electronically controlled. Printed copies are considered uncontrolled.

Confidential

8.5.2.1. Analysis Methods

A. Statistical Methodology

To compare the proportion of subjects that receive indicated therapy pre-intervention (Phase I) to the proportion post-intervention (Phase II), a Fisher's Exact test will determine statistical significance. A Fisher's exact test is recommended for smaller sample sizes. The proportion of subjects diagnosed will be evaluated at multiple time points because the time from diagnosis to implant is expected to vary by geography. Shorter time intervals will be used to evaluate the proportion of implants than for the proportion of diagnosis because time from diagnosis to implant is typically shorter than the time from enrollment to SND diagnosis. Thus, times are pre-specified starting at 3 months and any additional 3-month interval thereafter for which there is sufficient follow-up data available to compare study phases. Proportions calculated at all available time points will be reported. Additionally, a Poisson regression will compare the average number of subjects with an implant where the subject time in study beginning at the time of SND diagnosis is treated as an offset in the model. The above described tests will be performed only for the South Asia geography as described in Section 6. Further, similar tests will compare the differences in the types of therapy received in Phase I and Phase II. For example, a Fisher's exact test will compare the frequency of dual chamber device use pre- and post-intervention.

This document is electronically controlled. Printed copies are considered uncontrolled.

Confidential

B. Determination of Patients/Data for Analysis

Subjects that meet inclusion criteria and obtain an SND diagnosis shall be included in this analysis. The proportion estimates will be calculated based on information from fixed time points at 3 months of follow-up, 6 months of follow-up, and any additional 3-month interval thereafter for which there is sufficient follow-up data available to compare study phases. The number of subjects that obtain an IPG by pre-specified time point $t = 3, 6, \text{ etc.}$, will be included in the numerator and the number of subjects with an SND diagnosis will be included in the denominator.

C. Additional Analyses

- In addition to the overall diagnosis and treatment rates between Phase I and Phase II, various descriptive summaries of the subjects will be explored by geography, including the following:
 - The distribution of subgroups of final diagnoses that fall under the general categorization of SND –
 - The distribution of various diagnostic tests used to determine final diagnosis
 - The association between diagnostic tests used and the type of SND indication
 - A table that describes the type and number of devices prescribed for SND
 - A summary of pacing modes for devices prescribed for SND

8.5.2.2. Sample Size Methods and Assumptions

The proportion of IPG therapy in SND subjects is currently unknown within the study geographies. The PANARM HF study of 2000 subjects found that 146 out of 331 bradycardia subjects (44%) had symptomatic SND and that 15 (10%) of SND subjects opted for IPG therapy. PANARM HF included symptomatic HF which is different than the IMPROVE Brady population. Thus, the percentages expected in IMPROVE Brady may differ from those observed in PANARM HF. Assuming that 20% of subjects will be diagnosed with SND, this suggests that there will be 100 SND subjects in Phase I and 200 in Phase II per geography/country. Further assuming that IPG therapy will be adopted by 10% of SND subjects at three months after diagnosis, or equivalently an IPG incidence of 0.25 diagnoses per person-year, this means that the margin of error will be $\pm 8.0\%$ in a sample of 100 subjects per geography/country, based on a 95% confidence interval. If there are 100 SND subjects in Phase I and 200 SND subjects in Phase II, assuming a type I error of 0.05 and power of 0.90, a Fisher's Exact test will detect an increase in IPG therapy of at least 16% at three months after diagnosis. This means that the objective will obtain statistical significance if 52 of 200 SND subjects in Phase II opt for IPG therapy. The Poisson regression for the same scenario has a power of 0.95 to compare IPG incidence of 0.25 versus 0.625 implants per person-year. The power of this objective will improve if the percentage of SND diagnoses is larger than 20%. In order to better account for the proportion of SND diagnosis and IPG adoption per

This document is electronically controlled. Printed copies are considered uncontrolled.

Confidential

geography/country, the Phase II sample size will be recalculated within the geography/country once Phase I data collection is complete.

Stopping Guidelines for Futility

If Phase I of the study suggests that only 5% of enrolled subjects meet an SND indication and that only 5% of those indicated opt for IPG therapy, the study may close for futility at the end of Phase I within that geography/country. Suppose that the percent of SND diagnosis is 5% and that 5% of those indicated will opt for therapy. Assuming 500 subjects in Phase I, 5,440 subjects will be needed in Phase II to see an increase in the implant rate from 5% to 30%. This suggests a scenario with insufficient power to continue into Phase II.

[figure not shown]

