The proportion of IPG therapy in SND subjects is currently unknown within the study geographies. The PANARM HF study of 2000 subjects found that 146 out of 331 bradycardia subjects (44%) had SND and that 15 (10%) of SND subjects opted for IPG therapy. PANARM HF included symptomatic HF which is different than the IMPROVE Brady population. Thus, the percentages expected in IMPROVE Brady may differ from those observed in PANARM HF. Assuming that 20% of subjects will be diagnosed with SND, this suggests that there will be 100 SND subjects in Phase I and 200 in Phase II per geography/country. Further assuming that IPG therapy will be adopted by 10% of SND subjects at three months after diagnosis, or equivalently an IPG incidence of 0.25 diagnoses per person-year, this means that the margin of error will be $\pm 8.0\%$ in a sample of 100 subjects per geography/country, based on a 95% confidence interval. If there are 100 SND subjects in Phase I and 200 SND subjects in Phase II, assuming a type I error of 0.05 and power of 0.90, a Fisher's Exact test will detect an increase in IPG therapy of at least 16% at three months after diagnosis. This means that the objective will obtain statistical significance if 52 of 200 SND subjects in Phase II

opt for IPG therapy. The Poisson regression for the same scenario has a power of 0.95 to compare IPG incidence of 0.25 versus 0.625 implants per person-year. The power of this objective will improve if the percentage of SND diagnoses is larger than 20%. In order to better account for the proportion of SND diagnosis and IPG adoption per geography/country, the Phase II sample size will be recalculated within the geography/country once Phase I data collection is complete.

Stopping Guidelines for Futility

If Phase I of the study suggests that only 5% of enrolled subjects meet an SND indication and that only 5% of those indicated opt for IPG therapy, the study may close for futility at the end of Phase I within that geography/country. Suppose that the percent of SND diagnosis is 5% and that 5% of those indicated will opt for therapy. Assuming 500 subjects in Phase I, 5,440 subjects will be needed in Phase II to see an increase in the implant rate from 5% to 30%. This suggests a scenario with insufficient power to continue into Phase II.

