8.4. General Summaries

The Medtronic statistician who is assigned to the project will conduct all statistical analysis. Sample size package PASS 2008 was used for sample size evaluation. The two primary endpoints are the change in the proportion of subjects with an SND diagnosis after intervention and the change in the proportion of subjects receiving IPG therapy after intervention. In current practice, both of these proportions are unknown for a set of subjects meeting the study inclusion criteria. Three principles will guide the statistical analysis outlined below. The first principle is that the sample size calculations will use exact confidence intervals and tests to compare binomial proportions. The second principle of the analysis is that sample size calculations for Phase II of the study design will depend on the outcomes observed in Phase I of the study design. Due to this, the Phase II sample size calculations provided herein are preliminary calculations that will be amended once Phase I data collection is completed. In general the study will start with a 1:2 collection ratio for Phase I and Phase II sample sizes. Twice as many subjects are enrolled in Phase II of the study design so that the study may also examine any temporal drift in the outcomes of interest or subject demographics. The third principle of the analysis is that both the

This document is electronically controlled. Printed copies are considered uncontrolled.

Confidential

statistical methods and the sample size calculations will be geography specific because the study outcomes are expected to vary by geography.

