8.5.1.2. Sample Size Methods and Assumptions

The proportion of SND diagnoses in bradycardia subjects is currently unknown within the study geographies. The PANARM HF study of 2000 subjects found that 146 out of 331 bradycardia subjects (44%) had symptomatic SND and that 15 (10%) of SND subjects opted for IPG therapy (internal data on file). The power calculations conservatively assume that the SND diagnosis will be 20% at six months of follow-up, or equivalently an SND incidence of 0.4 diagnoses per person-year. Thus, the margin of error will be $\pm 4\%$ in a sample of 500 subjects per geography/country, based on a 95% confidence interval. If 500 subjects are collected in Phase I and 1000 subjects are collected in Phase II, assuming a type I error of 0.05 and power of 0.90, a chi-square test will detect an increase in SND diagnosis of at least 8%. For example, the study will find a statistically significant difference between a Phase I SND percentage of 20% at 6 months and a Phase II SND percentage of 28% at 6 months. The Poisson regression for the same scenario has a power of 0.95 to compare SND incidence of 0.4 versus 0.56 diagnoses per person-year. If the proportion of SND diagnoses is smaller than 20%, there will be more power to detect significant differences in the diagnosis proportion. Thus, the Phase II sample size will be recalculated within geography/country once Phase I data collection is complete. It is expected that the study attrition rate may be 10-15% of the study population. To account for attrition, *the sample size for Phase I will be 550 subjects per geography/country and for Phase II may be 1100 subjects per geography/country.*

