8.5.3.1. Analysis Methods

A. Statistical Methodology

An exact 95% confidence interval of a binomial proportion at each pre-determined time point will be used to calculate the margin of error for the SND and IPG proportions in Phase I of the study.

B. Determination of Patients/Data for Analysis

All subjects that are enrolled in the study will be included in the determination of the proportion estimates of SND. The proportion estimates will be calculated based on information from fixed time points at 6 months of follow-up, 12 months, and any additional 6-month interval thereafter for which there is follow-up data available. The number of subjects that obtain an SND diagnosis by pre-specified time point $t = 6, 12, \text{ etc.}$, is included in the numerator and the number of subjects enrolled is included in

This document is electronically controlled. Printed copies are considered uncontrolled.

Confidential

the denominator. The number of subjects that meet inclusion criteria and obtain an SND diagnosis shall be included in the determination of the proportion estimates of IPG therapy. The proportion estimates will be calculated based on information from fixed time points at 3 months of follow-up, 6 months, and any additional 3-month interval thereafter for which there is follow-up data available. The number of subjects that obtain an IPG by pre-specified time point $t = 3, 6, \text{ etc.}$, will be included in the numerator and the number of subjects with an SND diagnosis will be included in the denominator.

C. Additional Analyses

- In addition to the overall diagnosis and treatment rates of Phase I subjects, various descriptive summaries of the subjects will be explored by geography, including the following:
 - The distribution of subgroups of final diagnoses that fall under the general categorization of SND – overall and by local region
 - The distribution of various diagnostic tests used to determine final diagnosis
 - The association between diagnostic tests used and the type of SND indication
 - A table that describes the type and number of devices prescribed for SND
 - A summary of pacing modes for devices prescribed for SND

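### The stated ±8.0% margin of error for a 10% implant proportion in 100 SND subjects does not follow from the plan's exact method, which gives 4.9% to 17.6%

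*SAP*

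**What the plan says.** The sample size text for Primary Objective #2 (SAP 8.5.2.2, repeated in Protocol 11.1) expects that "there will be 100 SND subjects in Phase I and 200 in Phase II per geography/country". It assumes that "IPG therapy will be adopted by 10% of SND subjects at three months after diagnosis" and concludes that "the margin of error will be $\pm 8.0\%$ in a sample of 100 subjects". The Protocol words the basis the same way: "in a sample of 100 subjects per geography/country, based on a 95% confidence interval".

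The interval method is given elsewhere. SAP 8.4 lists as its first principle that "the sample size calculations will use exact confidence intervals and tests to compare binomial proportions", and Protocol section 11 states the same principle. For the Phase I proportions, SAP 8.5.3.1 says: "An exact 95% confidence interval of a binomial proportion at each pre-determined time point will be used to calculate the margin of error". Protocol 11.2 has the same method under Secondary Objective #1.

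The corresponding figure for the diagnosis proportion (20% assumed, SAP 8.5.1.2) is printed to a whole percent: "the margin of error will be $\pm 4\%$ in a sample of 500 subjects".

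**The concern.** The proportion, the number of subjects, the confidence level and the type of interval are all stated, so the margin can be recomputed. At 10% in 100 the usual normal-approximation margin is about 6 points, so ±8.0 looks too wide. A binomial interval this far from 50% is also not symmetric under the exact method, so a single ± value cannot describe it.

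The stake is modest. This is the precision quoted for the Phase I implant proportion at the assumed 10%. That proportion is reported under Secondary Objective #1 and is the control value for Primary Objective #2. A reader who relies on the printed figure would take the lower limit for an observed 10% to be 2.0%.

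**Working it through.** **Inputs**
- Assumed implant proportion 10% and n = 100, so x = 10 (SAP 8.5.2.2; Protocol 11.1).
- Confidence level 95% (same places). Two-sided is assumed, since sidedness is not stated.
- Exact binomial interval (SAP 8.4 and 8.5.3.1). Clopper-Pearson is assumed, since the documents say only exact.

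**Step 1: the plan's figure as printed.** 10% ± 8.0 points is 2.0% to 18.0%, total width 16.0 points.

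**Step 2: the plan's own method.** Clopper-Pearson limits are beta quantiles:
- lower = Beta(0.025; x, n − x + 1) = Beta(0.025; 10, 91) = 0.0490
- upper = Beta(0.975; x + 1, n − x) = Beta(0.975; 11, 90) = 0.1762

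The lower arm is 10.00 − 4.90 = 5.10 points and the upper arm is 17.62 − 10.00 = 7.62 points. The half-width is (17.62 − 4.90)/2 = 6.36 points.

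**Step 3: can another 95% interval for 10/100 reproduce 8.0?** The Wald margin is 1.96 × √(0.1 × 0.9/100) = 1.96 × 0.03 = 5.88 points. The continuity correction adds 1/(2 × 100) = 0.5 points, giving 6.38.

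| Interval | Half-width (points) | Upper arm (points) |
|---|---|---|
| Exact | 6.36 | 7.62 |
| Wald | 5.88 | 5.88 |
| Wald, continuity-corrected | 6.38 | 6.38 |
| Wilson | 5.96 | 7.44 |
| Wilson, continuity-corrected | 6.44 | 8.04 |
| Agresti-Coull | 6.13 | 7.61 |
| Jeffreys | 5.88 | 7.01 |

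No half-width reaches 8.0. One upper arm does, that of the continuity-corrected Wilson interval (5.16% to 18.04%), but its lower arm is 4.84, so it does not support a symmetric ±8.0 either. For a Wald margin of 8.0 at 10%, n would be (1.96/0.08)² × 0.09 ≈ 54, not 100.

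**Step 4: size of the discrepancy.**
- Against the exact half-width: 8.0/6.36 = 1.26, so 26% wider.
- Against the exact upper arm: 8.0/7.62 = 1.05, so 5% wider.
- Lower limit: 2.0% printed against 4.9% exact, 2.9 points too low.
- Upper limit: 18.0% printed against 17.6% exact, 0.4 points too high.

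**Step 5: the diagnosis figure.** For 100 of 500 the exact interval is 16.58% to 23.78%: lower arm 3.42, upper arm 3.78, half-width 3.60. Half-width and upper arm both round to the printed ±4%. That figure is therefore sound at its precision, but it does not show which convention the authors used for a margin.

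**Step 6: does anything depend on the margin?** Exact enumeration of Fisher's test for 10% v 26% with 100 v 200 subjects gives power 0.923, so the 16-point detectable increase at 90% power stands. The plan's example of 52 of 200 against 10 of 100 gives p = 0.0013. Neither calculation uses the margin.

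**The case against.** The strongest defence is that the documents never define the margin of error as a half-width. If it means the larger arm of an asymmetric interval, the exact value is 7.6, which rounds to 8. The diagnosis figure of ±4% fits that convention as well as the half-width one. The only fault would then be a surplus decimal, an excess of about 5% rather than 26%. This is a fair reading and it limits how serious the point can be. It does not rescue the text: the figure is printed as 8.0, the exact upper arm to one decimal is 7.6, and the ± sign implies a lower limit of 2.0% where the exact limit is 4.9%.

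A second defence is that the figure is a planning illustration which no longer governs anything. SAP section 6 was added after Phase I was complete in all geographies, and under SAP 8.5.3.1 the reported interval will be computed from the observed data. That is correct, and it is why the point is editorial.

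A reader might go further in ways the documents do not support:
- **That no standard interval can give 8.0.** The continuity-corrected Wilson upper arm is 8.04. Nothing shows that it was used, but the blanket statement is untrue.
- **That the 20% diagnosis assumption was carried into the 10% calculation.** For 20 of 100 the Wald margin is 7.84 and the exact half-width 8.26, which print as 7.8 and 8.3. Neither is 8.0, and the documents do not say how the figure arose.
- **That ±6.4 is the right replacement.** 10% ± 6.4 is 3.6% to 16.4%, which is not the exact interval and understates its upper limit.
- **That the margin drives the Phase II recalculation or the futility guideline.** SAP section 7 (Tables 2 to 4) works from SND and implant percentages as point values. The futility text in SAP 8.5.2.2 and the termination criteria in Protocol 10.2 are also written on percentages, with no confidence limit. The worked 5% case has 5% × 500 = 25 SND subjects, so a margin for 100 would not apply. Both 2.0% to 18.0% and 4.9% to 17.6% contain 5% in any case.

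**Conclusion.** The point holds as a minor arithmetic correction. Under the plan's stated inputs and exact method, the 95% interval for a 10% implant proportion in 100 SND subjects is 4.9% to 17.6% (−5.1/+7.6 points, half-width 6.4), not 10% ± 8.0. The printed interval contains the whole exact interval, so the error is conservative. No power, sample size, stopping or analysis result changes.

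This rests on a two-sided interval, on Clopper-Pearson as the exact method, and on all 100 SND subjects contributing to the three-month proportion, as the plan's own calculation assumes.

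**What to change.** In SAP 8.5.2.2 and in Protocol 11.1 (Primary Objective #2), replace ±8.0% with the exact 95% limits, 4.9% to 17.6% (−5.1/+7.6 points). Stating the limits also removes the question of which convention a single margin follows. For consistency, the ±4% in SAP 8.5.1.2 and Protocol 11.1 (Primary Objective #1) can be given as 16.6% to 23.8%. The cost is one corrected figure in each document, plus the optional companion edit, with no operational consequence.

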8.5.3. Secondary Objective #1

Describe the diagnosis and treatment of Phase I subjects.

8.5.3.1. Analysis Methods

A. Statistical Methodology

An exact 95% confidence interval of a binomial proportion at each pre-determined time point will be used to calculate the margin of error for the SND and IPG proportions in Phase I of the study.

B. Determination of Patients/Data for Analysis

All subjects that are enrolled in the study will be included in the determination of the proportion estimates of SND. The proportion estimates will be calculated based on information from fixed time points at 6 months of follow-up, 12 months, and any additional 6-month interval thereafter for which there is follow-up data available. The number of subjects that obtain an SND diagnosis by pre-specified time point $t = 6, 12, \text{ etc.}$, is included in the numerator and the number of subjects enrolled is included in

This document is electronically controlled. Printed copies are considered uncontrolled.

Confidential

the denominator. The number of subjects that meet inclusion criteria and obtain an SND diagnosis shall be included in the determination of the proportion estimates of IPG therapy. The proportion estimates will be calculated based on information from fixed time points at 3 months of follow-up, 6 months, and any additional 3-month interval thereafter for which there is follow-up data available. The number of subjects that obtain an IPG by pre-specified time point $t = 3, 6, \text{ etc.}$, will be included in the numerator and the number of subjects with an SND diagnosis will be included in the denominator.

C. Additional Analyses

- In addition to the overall diagnosis and treatment rates of Phase I subjects, various descriptive summaries of the subjects will be explored by geography, including the following:
 - The distribution of subgroups of final diagnoses that fall under the general categorization of SND – overall and by local region
 - The distribution of various diagnostic tests used to determine final diagnosis
 - The association between diagnostic tests used and the type of SND indication
 - A table that describes the type and number of devices prescribed for SND
 - A summary of pacing modes for devices prescribed for SND

8.5.4. Secondary Objective #2

Evaluate the change in the time to diagnosis of SND before and after intervention.

8.5.4.1. Analysis Methods

A. Statistical Methodology

A log-rank test of two Kaplan-Meier curves will determine if there is a significant difference in the time to diagnosis before and after intervention, within the South Asia geography. [REDACTED]

[REDACTED]

[REDACTED]

[REDACTED]

Cox models may also be fit to examine independent variables of interest that may affect SND diagnosis, such as gender and age. Descriptive statistics will be used to characterize the number of visits that occur before an SND diagnosis and further will examine number of visits separated by Phase, type of enrolling physician, and possibly other baseline characteristics. [REDACTED]

This document is electronically controlled. Printed copies are considered uncontrolled.

Confidential

B. Determination of Patients/Data for Analysis

The subjects to include in the analysis of Secondary Objective 2 in Section **Error! Reference source not found.** are the same as specified in Section **Error! Reference source not found.** for Primary Objective 1.

C. Additional Analyses

In addition to the time to event analysis, various additional analyses of the subjects will be explored, including a description of diagnostic tests performed when there is a delay in a patient's diagnosis. The endpoint is time to diagnosis and variables of interest are the different types of diagnostic tests. A table will be created with a format as follows:

Tests performed	SND dx 0-6 months	SND dx 6-12 months	SND dx 12-18 months
ECG	Number of tests, number of subjects		
Tilt table			
ILR			
Holter			
Average number of tests performed			

